The maintenance dose of REGN4461 has changed from mg QW to mg QW.	New data from the ongoing REGN4461-GLD-1875 study in patients with generalized lipodystrophy (GLD) have emerged since this protocol was finalized. Lower observed drug concentrations in these patients suggest that GLD patients (who have very low leptin levels) have faster REGN4461 clearance than expected based on the FIH study (REGN4461-HV-1794) that was used as the basis for the PK model in both the familial partial lipodystrophy (FPLD) and GLD studies. Given the uncertainty surrounding PK in patients with FPLD (that share a characteristic with GLD patients of having low leptin levels), and the desire to ensure drug concentrations are in the fully therapeutic range, the dose is being increased to ensure study patients achieve a Ctrough that saturates target-mediated clearance at approximately the same serum concentrations as targeted with the original dose of mg QW. This dose was determined using an updated PK model based on all available data. While excess weight loss is unlikely in FPLD, a dose modification rule was added for the dose to be reduced from mg to mg during Treatment Period 2 (weeks 13-24) in case of excessive weight loss.	Clinical Study Protocol Synopsis – Treatment Section 1 Introduction Section 3.2.2 Rationale for Dose Selection Section 6.1 Study Description and Duration Figure 2 Study Flow Diagram Section 8.1 Investigational and Reference Treatments Section 8.4.1 Dose Modification

Description of Change	Brief Rationale	Section # and Name
Patients screened under the original protocol may re-screen for HbA1c and triglycerides (the only parameters required to be repeated) before entering the run-in period to reconfirm eligibility if the screening window (up to 10 weeks) has been exceeded.	In the GLD study there were large changes observed in TGs and HbA1c during the screening period. If the screening period is extended, we need to ensure patients still meet the eligibility criteria for the study.	Section 6.1 Study Description and Duration Section 9.1.1 Footnotes for the Schedule of Events Table 1: Screening and Placebo Run-in, Footnote 1 Appendix 1 Hemoglobin A1C, Triglyceride and Leptin Measurements
Removed the sentence that imaging data will be destroyed after 15 years.	Destruction of material after 15 years only applies to biological samples.	Section 9.2.2.11 Assessment of Hepatic Fat Content and Liver Size
The definition of baseline has been added to the Statistical Methods.	The definition was missing in the prior version of the protocol.	Section 11.4 Statistical Methods

LIST OF ABBREVIATIONS AND DEFINITIONS OF TERMS

Abbreviation Definition/Term
ADA Anti-drug antibody

ADIPO-IR Adipose Insulin Resistance

AE Adverse event

AESI Adverse event of special interest

ALT Alanine aminotransferase
ANGPTL3 Angiopoietin-like protein 3
APLD Acquired partial lipodystrophy

ApoC3 Apolipoprotein C3

AST Aspartate aminotransferase

AUC Area under the curve BMI Body mass index

BPI-SF Brief Pain Inventory – Short Form

CLIA Clinical Laboratory Improvement Amendments

C_{max} Maximum observed concentration

COVID-19 Coronavirus Disease 2019
CPK Creatine phosphokinase

CRF Case report form (electronic or paper)

CRO Contract research organization

 C_{trough} Trough concentrations DNA Deoxyribonucleic acid

DXA Dual-energy X-ray absorptiometry

EC Ethics Committee
ECG Electrocardiogram

(e)COA (electronic) Clinical Outcomes Assessment

EDC Electronic data capture

ELISA Enzyme Linked Immunosorbent Assay

FAS Full analysis set

FBR Future biomedical research
FDA Food and Drug Administration

FFA Free fatty acids
FIH First-in-human

FPLD Familial partial lipodystrophy

GCP Good Clinical Practice
GLD Generalized lipodystrophy

GPS Global Patient Safety

HADS Hospital anxiety and depression scale

HbA1c Hemoglobin A1c
HBV Hepatitis B virus
HCV Hepatitis C virus

HDL High-density lipoprotein

HIV Human immunodeficiency virus

HOMA-IR Homeostatic Model Assessment for Insulin Resistance

ICF Informed consent form

ICH International Council for Harmonisation

INR International normalized ratio

IP Investigational product
IRB Institutional Review Board

IV Intravenous

LDH Lactate dehydrogenase
LDL Low-density lipoprotein

LEPR Leptin receptor

LIPO-IR Lipoprotein Insulin Resistance Index

LLN Lower limit of normal

MD Multiple doses

MMTT Mixed meal tolerance test
MRI Magnetic resonance imaging

MRI-PDFF Magnetic resonance imaging-derived proton density fat fraction

NHANES National Health and Nutrition Examination Survey

NIH National Institutes of Health NODM New onset of diabetes mellitus

PBO Placebo run-in period

PCR Polymerase chain reaction

PD Pharmacodynamic

PGIS Patient Global Impression of Severity

PHQ-8 8-item patient health questionnaire depression scale

PK Pharmacokinetic

PKAS Pharmacokinetic Analysis Set

PLD Partial lipodystrophy
PRO Patient reported outcome

13.3.	Patients Confidentiality and Data Protection	97
13.4.	Institutional Review Board/Ethics Committee	98
13.5.	Clinical Study Data Transparency	98
14.	PROTOCOL AMENDMENTS	99
15.	PREMATURE TERMINATION OF THE STUDY OR CLOSE-OUT OF A SITE	100
15.1.	Premature Termination of the Study	100
15.2.	Close-out of a Site	100
16.	CONFIDENTIALITY	100
17.	FINANCING AND INSURANCE	100
18.	PUBLICATION POLICY	100
19.	REFERENCES	101
20.	INVESTIGATOR'S AGREEMENT	104
CICNIAT	TIDE OF SDONSOD'S DESDONSIBLE OFFICEDS	107

LIST OF TABLES

Table 1:	Schedule of Events: Screening and Placebo Run-In	57
Table 2:	Schedule of Events: TP1, TP2 and Off-Drug Follow up	62
Table 3:	Table 3: Half-Width of the 90% Confidence Interval for Primary Endpoints	
	LIST OF FIGURES	
Figure 1:	Preliminary Mean (±SD) Concentrations of Total REGN4461 in Serum by Nominal Time and Treatment Arm in Patients with Generalized Lipodystrophy (Study R4461-GLD-1875; PKAS)	33
Figure 2:	Study Flow Diagram	42
Figure 3:	Screening Triglyceride and Hemoglobin A1c Measurements	105
	LIST OF APPENDICES	
APPEND	IX 1. HEMOGLOBIN A1C, TRIGLYCERIDE AND LEPTIN	105

CLINICAL STUDY PROTOCOL SYNOPSIS

Title	A Randomized Double-Blind Placebo-Controlled Study of the LEPR Agonist Antibody REGN4461 for the Treatment of Metabolic Abnormalities in Patients with Familial Partial Lipodystrophy	
Site Locations	This is a multicenter study that will take place globally.	
Principal Investigator		
Objectives	Primary Objectives	
	The primary objectives will be evaluated for patients in cohort A (leptin $<8.0 \text{ ng/ml}$) only:	
	 To evaluate the effect of REGN4461 on fasting triglycerides (TG) in patients with baseline leptin <8.0 ng/mL with elevated baseline fasting TG (>200 mg/dL) 	
	 To evaluate the effect of REGN4461 on hyperglycemia in patients with baseline leptin <8.0 ng/mL with elevated baseline hemoglobin A1c (HbA1c; >7.0%) 	
	Secondary Objectives	
	The following secondary objectives of the study will be evaluated for cohort B and for the combined set of cohorts A plus B:	
	 To evaluate the effect of REGN4461 on fasting TG levels in patients with hypertriglyceridemia (fasting TG >200 mg/dL). 	
	 To evaluate the effect of REGN4461 on glycemic control in patients with hyperglycemia (HbA1c >7.0%) 	
	The following secondary objectives of the study will be evaluated for cohorts A and B separately, and for the combined set of cohorts A plus B:	
	• To evaluate the effect of REGN4461 on liver fat in patients with hepatic steatosis (baseline Hepatic Fat Fraction [Magnetic resonance imaging-derived proton density fat fraction, MRI-PDFF] ≥8.5%)	
	To evaluate the effect of REGN4461 on hunger	
	To evaluate safety and tolerability of REGN4461	
	To characterize the concentration profile of REGN4461 over time	
	To assess immunogenicity to REGN4461	

Study Design

This is a phase 2, randomized, double-blind, placebo-controlled study of the efficacy and safety of REGN4461 in patients with familial partial lipodystrophy (FPLD) and metabolic abnormalities (elevated fasting TG with or without elevated HbA1c) who are not receiving recombinant human leptin (rhLeptin) therapy.

Patients 18 years of age or older with a clinical diagnosis of FPLD will undergo screening, including measurement of HbA1c, fasting TG, and leptin levels. A diagnosis of FPLD requires either a documented ClinVar pathogenic or likely pathogenic variant in a known FPLD gene or pathognomonic regional lipoatrophy by dual-energy X-ray absorptiometry (DXA). In addition, patients must have metabolic abnormalities (hypertriglyceridemia with or without hyperglycemia) and serum leptin level ≤20.0 ng/mL to be included.

The study comprises a screening period lasting up to 10 weeks, a 4-week single-blind placebo run-in period (PBO), a 12-week double-blind placebo-controlled treatment period (TP1), a 12-week single-blind treatment period (TP2) during which all patients receive REGN4461, and a 16-week off-drug safety follow-up period.

Patients will first be assigned to 1 of 2 cohorts based on baseline leptin levels at screening (cohort A: leptin <8.0 ng/mL; cohort B: leptin 8.0 to ≤ 20.0 ng/mL).

These cohorts will then be randomized 1:1 into the following study arms:

- Study arm 1: patients randomized to receive placebo for 12 weeks (TP1) followed by crossover to REGN4461 treatment for 12 weeks (TP2).
- Study arm 2: patients randomized to receive REGN4461 treatment for 24 weeks (TP1 and TP2).

Randomization will be stratified according to HbA1c at screening (HbA1c <7.0% or HbA1c >7.0%) within each cohort.

Study Duration	Study duration is up to 54 weeks.
End of Study Definition	The end of study is defined as the date the last patient either completes the last study visit, withdraws from the study, or is lost to follow-up (ie, the study patient can no longer be contacted by the investigator).
Population	
Sample Size:	Up to 40 patients will be enrolled.
Target Population:	Adult patients with a clinical diagnosis of FPLD, leptin ≤20.0 ng/mL and

metabolic abnormalities who are not currently treated with rhLeptin.

Treatment

Study Drug

REGN4461

Dose/Route:

mg/kg intravenously (IV) loading dose followed by weekly (QW) doses of mg subcutaneously (SC).

Reference Drug

Dose/Route:

Placebo matching REGN4461 is prepared in the same formulation without the addition of REGN4461.

Schedule:

Single-blind run-in period:

All patients will receive an IV placebo infusion, followed by placebo SC QW injections administered subsequently for 3 weeks.

Treatment period 1 (TP1):

- Study arm 1: IV placebo infusion on day 1 followed by SC QW injections of placebo for 11 weeks starting on day 8
- Study arm 2: IV REGN4461 (mg/kg) infusion on day 1 followed by SC injections of REGN4461 (mg QW) for 11 weeks starting on day 8

Treatment Period 2 (TP2):

- Study arm 1: IV REGN4461 (mmg/kg) infusion and SC placebo on day 85, followed by SC injections of REGN4461 (mmg QW) for 11 weeks starting on day 92
- on day 85, followed by SC injections of REGN4461 (mg) mg QW) for 11 weeks starting on day 92

Endpoints

Co-Primary:

- Percent change in fasting serum TG from baseline to week 12 in patients with elevated baseline fasting TG (>200 mg/dL) and with baseline leptin <8.0 ng/mL (cohort A)
- Absolute change in HbA1c from baseline to week 12 in patients with elevated baseline HbA1c (>7.0%) and with baseline leptin <8.0 ng/mL (cohort A)

Secondary:

Note: Patients in study arm 1 must meet stability criteria during TP1 (a change in $HbA1c \le 0.5$ percentage points and a change in $TG \le 25\%$) to be included for specific endpoints as indicated below.

The following secondary endpoints will be analyzed for cohort B and for the combined set of cohorts A plus B:

Regeneron Pharmaceuticals, Inc.

- Percent change in fasting serum TG from baseline to week 12 in patients with elevated baseline fasting TG (>200 mg/dL)
- Absolute change in HbA1c from baseline to week 12 in patients with elevated baseline HbA1c (>7.0%)

The following secondary endpoints will be analyzed for cohorts A and B separately, and for the combined set of cohorts A plus B:

- Percent change in fasting serum TG from baseline to week 12 compared to the percent change between week 12 and week 24 (study arm 1)
- Percent change in fasting serum TG from baseline to week 24 (study arm 2)
- Percent change in fasting serum TG after the first 12 weeks of exposure to REGN4461— from baseline to week 12 (study arm 2) and from week 12 to week 24 (study arm 1; patients must meet stability criteria)
- Change in HbA1c from baseline to week 12 compared to the change between week 12 and week 24 (study arm 1)
- Change in fasting glucose from baseline to week 12 compared to the change between week 12 and week 24 (study arm 1)
- Change in HbA1c from baseline to week 24 (study arm 2)
- Change in fasting glucose from baseline to week 24 (study arm 2)
- Change in HbA1c from baseline to week 12 (study arm 2) and from week 12 to week 24 (study arm 1; patients must meet stability criteria)
- Change in fasting glucose from baseline to week 12 (study arm 2) and from week 12 to week 24 (study arm 1)
- Percent change in liver fat (MRI-PDFF) from baseline to week 12, REGN4461 versus placebo in patients with baseline liver fat (MRI-PDFF) ≥8.5%.
- Percent change in liver fat (MRI-PDFF) from baseline to week 12 compared to the percent change between week 12 and week 24 (study arm 1) in patients with baseline liver fat (MRI-PDFF) >8.5%.
- Percent change in liver fat (MRI-PDFF) from baseline to week 24 (study arm 2) in patients with baseline liver fat (MRI-PDFF) ≥8.5%.

- Percent change in liver fat (MRI-PDFF) from baseline to week 12 (study arm 2) and from week 12 to week 24 (study arm 1) in patients with baseline liver fat (MRI-PDFF) ≥8.5%.
- Change on the daily lipodystrophy hunger questionnaire from baseline to week 12 and week 24
- The incidence and severity of treatment-emergent adverse events (TEAEs)
- Concentrations of REGN4461 in serum over time
- Immunogenicity of REGN4461 as determined by the incidence, titer and clinical impact of treatment-emergent anti-drug antibodies (ADAs) to REGN4461, over time compared to placebo

Procedures and Assessments

The following procedures will be performed for the sole purpose of determining study eligibility or characterizing the baseline characteristics of the study population: medical history, demographics, human immunodeficiency virus (HIV) serology, and hepatitis testing (hepatitis B surface antigen [HBsAg] and hepatitis C virus [HCV]), menstrual history, and pregnancy status.

Efficacy procedures include: fasting TG assessment, fasting glucose assessment, HbA1c, fructosamine, insulin, lipid panel, urine creatinine and albumin, insulin sensitivity measurement, lipoprotein analysis by NMR, whole body composition by DXA, bioimpedance, liver volume and fat content by MRI, and patient-reported outcomes.

Safety procedures include: body weight, height, vital signs, physical examination, menstrual history/pregnancy status reporting/ confirmation of contraception, and electrocardiogram (ECG).

Laboratory procedures include: blood chemistry, hematology, lipid panel, urinalysis, pregnancy testing, and other laboratory testing.

Statistical Plan

No formal statistical hypothesis testing will be performed for this study.

The size of the study is determined by feasibility assessments. Due to the limited number of identified PLD patients with low leptin and moderate metabolic abnormalities, up to 40 patients will be enrolled.

With a total of 40 patients (20 per cohort, randomized in the ratio of 1:1 into REGN4461 arm and placebo arm), the primary analysis will be carried out on the 20 patients in lower leptin cohort A in TP1. Not all patients will necessarily have HbA1c >7.0%, ie, not all of the patients will be assessed for the HbA1c endpoint. From the feasibility work, it is estimated that 78% of the patients will have elevated baseline HbA1c. With 20 patients in cohort A (10 patients per study arm), the half-width of the 90% confidence

interval in change from baseline to week 12 between the REGN4461 arm and the placebo arm for HbA1c is 1.4 percentage points, assuming the standard deviation (SD) of 1.81 %. For the TG, the half-width of the 90% confidence interval in logarithm transformed geometric mean ratio (GMR) (REGN4461 week12/baseline divided by placebo week12/baseline) is 0.67, assuming the SD for logarithm transformed fasting TG is 0.87. The SD is estimated from the subset samples of the extracted National Institutes of Health (NIH) study data.

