2.2. Secondary Objectives

The following secondary objectives of the study will be evaluated for cohort B and for the combined set of cohorts A plus B:

- To evaluate the effect of REGN4461 on fasting TG levels in patients with hypertriglyceridemia (fasting TG >200 mg/dL)
- To evaluate the effect of REGN4461 on glycemic control in patients with hyperglycemia (HbA1c >7.0%)

The following secondary objectives of the study will be evaluated for cohorts A and B separately, and for the combined set of cohorts A plus B:

- To evaluate the effect of REGN4461 on liver fat in patients with hepatic steatosis (baseline Hepatic Fat Fraction [Magnetic resonance imaging-derived proton density fat fraction, MRI-PDFF] ≥8.5%)
- To evaluate the effect of REGN4461 on hunger
- To evaluate safety and tolerability of REGN4461
- To characterize the concentration profile of REGN4461 over time
- To assess immunogenicity to REGN4461

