Patients with either moderate abnormalities of both HbA1c (>7.0%) and TG (>200 mg/dL), or a more severe abnormality of TG (>450 mg/dL), with normal or mildly abnormal HbA1c (up to 7.0%) are included. These inclusion criteria are met by the majority of FPLD patients and allow for separate analysis of REGN4461 treatment effects on each metabolic parameter.

The study includes adult patients only. Familial PLD is generally a progressive disease with pubertal onset of fat loss and a long delay between signs/symptoms and diagnosis. As such there is not a large population of pediatric patients with high unmet medical need.

Rationale for Study Endpoints:

The co-primary endpoints are the change in TG from baseline to week 12, and the change in HbA1c from baseline to week 12 in patients in cohort A. These co-primary endpoints were specifically selected because improvements in either or both parameters would help address the highest unmet medical need for PLD patients.

Significant heterogeneity in the response of fasting TG and HbA1c was observed in the metreleptin clinical trials. Given the uncertainty in treatment effect in FPLD patients and the limited number of FPLD patients, secondary endpoints include within-group analyses of all patients receiving their first 12 weeks of REGN4461. This includes individuals in study arm 1 (TP2) and study arm 2 (TP1). In addition, for Study Arm 1, the within group change for TP1 (placebo treatment) will be compared to TP2 (REGN4461 treatment).

The secondary endpoints also include analyses of fasting TG and HbA1c in the higher leptin cohort B. While data from Part B of REGN4461-HV-1794 suggest that a leptin level <8.0 ng/mL might identify individuals most likely to respond, some data suggest response to LEPR agonism in individuals with higher serum leptin, up to 20.0 ng/mL. Analyses of responses in cohort B will therefore allow for more accurate determination of a REGN4461-responsive patient population.

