3.2.3. Rationale for Analysis

The primary analyses are between-group comparisons (change in REGN4461 arm between baseline and week 12 versus change in placebo arm between baseline and week 12). The HbA1c and TG endpoints will be analyzed only in those individuals with corresponding pre-specified elevated baseline values. This will maximize our ability to determine treatment effects in a small study with heterogeneous baseline characteristics and inclusion criteria (Section 7.2.1).

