4.2. Secondary Endpoints

Note: Patients in study arm 1 must meet stability criteria during TP1 (a change in $HbA1c \le 0.5$ percentage points and a change in $TG \le 25\%$) to be included for specific endpoints as indicated below.

The following secondary endpoints will be analyzed for cohort B and for the combined set of cohorts A plus B:

- Percent change in fasting serum TG from baseline to week 12 in patients with elevated baseline fasting TG (>200 mg/dL)
- Absolute change in HbA1c from baseline to week 12 in patients with elevated baseline HbA1c (>7.0%)

The following secondary endpoints will be analyzed for cohorts A and B separately, and for the combined set of cohorts A plus B:

- Percent change in fasting serum TG from baseline to week 12 compared to the percent change between week 12 and week 24 (study arm 1)
- Percent change in fasting serum TG from baseline to week 24 (study arm 2)
- Percent change in fasting serum TG after the first 12 weeks of exposure to REGN4461— from baseline to week 12 (study arm 2) and from week 12 to week 24 (study arm 1; patients must meet stability criteria)
- Change in HbA1c from baseline to week 12 compared to the change between week 12 and week 24 (study arm 1)
- Change in fasting glucose from baseline to week 12 compared to the change between week 12 and week 24 (study arm 1)
- Change in HbA1c from baseline to week 24 (study arm 2)
- Change in fasting glucose from baseline to week 24 (study arm 2)
- Change in HbA1c from baseline to week 12 (study arm 2) and from week 12 to week 24 (study arm 1; patients must meet stability criteria)
- Change in fasting glucose from baseline to week 12 (study arm 2) and from week 12 to week 24 (study arm 1)

- Percent change in liver fat (MRI-PDFF) from baseline to week 12, REGN4461 versus placebo in patients with baseline liver fat (MRI-PDFF) ≥8.5%.
- Percent change in liver fat (MRI-PDFF) from baseline to week 12 compared to the percent change between week 12 and week 24 (study arm 1) in patients with baseline liver fat (MRI-PDFF) ≥8.5%.
- Percent change in liver fat (MRI-PDFF) from baseline to week 24 (study arm 2) in patients with baseline liver fat (MRI-PDFF) ≥8.5%.
- Percent change in liver fat (MRI-PDFF) from baseline to week 12 (study arm 2) and from week 12 to week 24 (study arm 1) in patients with baseline liver fat (MRI-PDFF) ≥8.5%.
- Change on the daily lipodystrophy hunger questionnaire from baseline to week 12 and week 24

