Table 4. Summary of Descriptive Statistics for Patients Randomized to REGN4461 in Normally-distributed Secondary Endpoints for the combined DBTP and SBTP Analysis

NOTE: These descriptive statistics will be presented three times, specifically in Cohort A, Cohort B, and Cohort A+B.

Endpoint		Descriptive Statistics
•	Absolute change in HbA1c from baseline to week 24	For Arm 2, descriptive summaries will be provided at each protocol specified visit up to week 24; mean changes (±SE) will be plotted across visits by treatment group; a spaghetti plot will be provided for individual patient data across visits by treatment group. These descriptive statistics will be provided twice, specifically for patients with baseline HbA1c>7% and again for All Patients.
•	Change in fasting glucose from baseline to week 24	For Arm 2, descriptive summaries will be provided at each protocol specified visit up to week 24; mean changes (±SE) will be plotted across visits by treatment group; a spaghetti plot will be provided for individual patient data across visits by treatment group. These descriptive statistics will be provided twice, specifically for patients with baseline HbA1c>7% and again for All Patients.
•	Percent change in liver fat (MRI-PDFF) from baseline to week 24	For patients with hepatic steatosis (baseline MRI-PDFF ≥8.5%) in Arm 2, descriptive summaries will be provided at each protocol specified visit up to week 24; mean changes (±SE) will be plotted across visits by treatment group; a spaghetti plot will be provided for individual patient data across visits by treatment group.

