# Table 5. Summary of Descriptive Statistics in Normally Distributed Secondary Endpoints based on REGN4461 Exposure

NOTE: Efficacy data for study treatment arm 1 (placebo) and arm 2 (REGN4461) will be combined by re-aligning to the first REGN4461 treatment administration, specifically study day 1 for arm 2 and week 12 for arm 1 will become REGN4461 Day 1. These descriptive statistics will be presented three times, specifically in Cohort A, Cohort B, and Cohort A+B.

Endpoints	Descriptive Statistic	
Absolute change in HbA1c from baseline to week 12	HbA1c mean changes from REGN4461     Day 1 to REGN4461 week 12 for combined DBTP-stable Arm 1 patients and Arm 2 patients will be provided along	

Regeneron Pharmaceuticals, Inc.

Page 38 of 88

Protocol: R4461-PLD-20100

• Absolute change in HbA1c from week 12 to week 24	with its corresponding 95% confidence interval.

 
Change in fasting glucose from baseline to week 12
 
Change in fasting glucose from week 12 to week 24
 
	• Fasting glucose mean changes from REGN4461 Day 1 to REGN4461 week 12 for combined Arm 1 and Arm 2 patients will be provided along with its corresponding 95% confidence interval.

 
Percent change in liver fat (MRI-PDFF) from baseline to week 12
 
Percent change in liver fat (MRI-PDFF) from week 12 to week 24
 
	• Liver fat (MRI-PDFF) mean changes from REGN4461 Day 1 to REGN4461 week 12 for combined Arm 1 and Arm 2 in patients with hepatic steatosis (baseline MRI-PDFF ≥8.5%) will be provided along with its corresponding 95% confidence interval.

Table 6. Summary of Statistics for Patients Randomized to Placebo in Normally distributed Secondary Endpoints

NOTE: These statistical estimates and descriptive statistics will be presented three times, specifically in Cohort A, Cohort B, and Cohort A+B.

Endpoints	Estimates	Comparison

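### The pooled first-12-weeks-on-drug HbA1c and fasting glucose results are not limited to HbA1c >7.0%, the population that the glycaemic objectives name

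*Protocol*

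**What the plan says.** Protocol Section 4.2 and the synopsis define two glycaemic endpoints over the first 12 weeks on drug:

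- HbA1c: "Change in HbA1c from baseline to week 12 (study arm 2) and from week 12 to week 24 (study arm 1", where the only condition is that Arm 1 was stable during TP1.
- Fasting glucose: "Change in fasting glucose from baseline to week 12 (study arm 2) and from week 12 to week 24 (study arm 1", with no condition at all.

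Section 11.4.3.2 adds only the stability rule, which limits change during TP1 and not the level of HbA1c.

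SAP Table 5 follows this. Its HbA1c row pools stable Arm 1 patients with Arm 2. Its glucose row gives "Fasting glucose mean changes from REGN4461 Day 1 to REGN4461 week 12 for combined Arm 1 and Arm 2 patients". Neither names an HbA1c subgroup, whereas the liver-fat row of the same table is limited to baseline MRI-PDFF ≥8.5%. Table 4, for week 24, reports HbA1c and glucose twice, "specifically for patients with baseline HbA1c>7% and again for All Patients".

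The secondary objective is "To evaluate the effect of REGN4461 on glycemic control in patients with hyperglycemia (HbA1c >7.0" per cent, for Cohort B and for A plus B. The primary objective in Section 2.1 sets the same threshold for Cohort A. Section 3.2.3 states: "The HbA1c and TG endpoints will be analyzed only in those individuals with corresponding pre-specified elevated baseline values". On eligibility, Section 3.2.1 says that patients with "a more severe abnormality of TG (>450 mg/dL), with normal or mildly abnormal HbA1c (up to 7.0%) are included".

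**The concern.** Neither the primary nor the secondary objectives ask about glycaemic control in patients at or below 7.0%, yet the pooled rows include them. These patients have less room for HbA1c to fall, so a simple mean over everyone is likely to understate the change in the population the objective names. TG does not raise the same issue, because both entry routes require TG >200 mg/dL.

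The pooling is there to draw more information on the drug effect from a small trial. Table 5 gives unmodelled means with confidence intervals and no adjustment for HbA1c stratum, so the patients included decide what the number means.

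The protocol text also pulls two ways. The endpoint rationale in Section 3.2.1 says the within-group analyses take in every patient's first 12 weeks on drug, while Section 3.2.3 confines HbA1c endpoints to patients with elevated baseline values.

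**Working it through.** **Inputs**, all from protocol Section 11.2 and its Table 3 (repeated in SAP Section 2.2) unless stated:

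- Share with HbA1c >7.0%: p = 0.78, so 0.22 at or below.
- On-drug HbA1c effect: -1.18 points (-0.98 after adjusting for placebo).
- SD for HbA1c: 1.81 points.
- Planned size: 20 per cohort, 40 in total (Section 7.1).
- Effect in patients ≤7.0%, as a fraction f of the effect above 7.0%: not in the documents. Assumed 0, 0.25 and 0.5.

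**1. Reproduce the plan's figures.** The 90% half-width for the between-arm difference is t(0.95, 2n-2) × SD × √(2/n).

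- n = 10: 1.404 (stated 1.4)
- n = 8: 1.594 (stated 1.59)
- n = 7: 1.724 (stated 1.72)

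The HbA1c figures reproduce, and 1.81 is being used as an SD of change.

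**2. Expected unrestricted mean.** Pooled mean = -1.18 × [p + (1 - p) × f].

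| f | Calculation | Mean change | Smaller by |
|---|---|---|---|
| 0 | -1.18 × 0.78 | -0.92 | 22% |
| 0.25 | -1.18 × (0.78 + 0.055) | -0.985 | 16.5% |
| 0.5 | -1.18 × (0.78 + 0.11) | -1.05 | 11% |

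The shift is 1.18 - 1.05 = 0.13 to 1.18 - 0.92 = 0.26 points. With f = 0, varying p from 0.60 to 0.90 changes the loss from 40% to 10%.

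**3. Precision given up by restricting.** The 95% half-width for a within-group mean is t(0.975, n-1) × 1.81 / √n. The same SD is kept in both displays, and stability exclusions are not yet counted.

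- One cohort: n = 20 gives 0.85. With 0.78 × 20 = 15.6, about 16, it is 0.96.
- Cohorts A plus B: n = 40 gives 0.58. With 0.78 × 40 = 31.2, about 31, it is 0.66.

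**4. Fasting glucose.** The documents give no glucose effect and no SD, so no figure can be computed.

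**The case against.** The best defence is that all patients were intended. Section 3.2.1 describes the within-group analyses that way, and in Section 4.2 every liver-fat bullet carries its threshold while no arm-specific HbA1c or glucose bullet does. This has some force. However, Section 3.2.1 goes on to explain its phrase as meaning both arms, and the stability filter already means that not every patient is counted for HbA1c.

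Section 3.2.3 is not decisive either. Its sentence follows one about the primary analyses and does not name fasting glucose. The glucose case therefore rests on the objectives and on Table 4.

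The size is also open to challenge. The documents do not say that -1.18 comes from patients above 7.0%; if the source was mixed, multiplying by 0.78 counts the dilution twice. The 0.13 to 0.26 point shift is small beside half-widths of 0.58 to 0.85. These reservations stand.

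Four stronger readings are tempting but not supported:

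- A reader might infer that Table 5 alone departs from a >7.0% rule. The Table 6 glucose row states no stratum either. Table 3 reads its estimates at >7.0% from a model like that in SAP Section 5.7.1.2, which is fitted to both strata without a treatment-by-stratum term, so patients ≤7.0% contribute to its treatment difference.
- A reader might infer that Table 5 cannot be compared with the other tables. Table 4 also has an all-patient display.
- A reader might infer that the stability rule strongly enriches Arm 1 for patients ≤7.0%. Quantifying this needs an SD of change at or below 7.0%, which the documents do not give; a two-sided reading of the 0.5-point limit, which they do not settle; and the effect of the TG criterion that must also be met.
- A reader might take the added patients to have normal glycaemia. The protocol says normal or mildly abnormal, and its new-onset diabetes criterion (Section 10.1.3) starts at HbA1c 6.5%.

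**Conclusion.** The gap is real and worth closing, but it is modest. The pooled HbA1c and glucose rows do not match the population in the objectives, and for HbA1c they conflict with the wording of Section 3.2.3. On the plan's own inputs, the unrestricted mean HbA1c change would be about 11% to 22% smaller than in patients >7.0%. This assumes that -1.18 is the effect in those patients, that 78% of the pool exceeds 7.0%, and that the rest have none to half of that effect. The glucose discrepancy is one of definition only, with no size that can be given.

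The consequences are limited. The endpoints are secondary and descriptive, and no formal testing is planned. After early termination, SAP Section 1.2.4 keeps only descriptive summaries and plots for efficacy, so it is not certain that the pooled means with confidence intervals will be produced.

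**What to change.** In SAP Table 5, give the HbA1c and fasting glucose rows (mean change, 95% CI) for patients with screening HbA1c >7.0% and again for all patients. Use the screening value: it is the randomisation stratum, and SAP Section 1.2.4 already adopts it for the HbA1c subgroup. State the stratum in the Table 6 glucose row. Add the threshold to the matching bullets in protocol Section 4.2 and the synopsis, and reconcile the Section 3.2.1 rationale with Section 3.2.3.

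The cost is document edits and one more display. The restricted row has fewer patients, with a 95% half-width of about 0.96 against 0.85 for one planned cohort. The stability exclusions may leave few Arm 1 patients in its HbA1c part. Keeping the all-patient row means no information is lost.
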